5.2. Safety assessments

Adverse Events

All AEs should be assessed starting after the subject signs the informed consent document (ICD) until 30 days after treatment discontinuation. Adverse events that lead to study discontinuation should be followed until resolution or stabilization.

Serious Adverse Events

Serious adverse events, regardless of relationship to the IP (POM, DARA, or Dex), that occur from the time the subject signs the ICD to at least 30 days after treatment discontinuation and those made known to the investigator at any time thereafter that are suspected of being related to the IP (POM, DARA, or Dex) must be reported to Janssen Drug Safety within 24 hours of the investigator's knowledge of the event.

Echocardiography and Electrocardiography

An echocardiogram or multiple gated acquisition (MUGA) scan to assess baseline cardiac function and risk of cardiac dysfunction, including cardiomyopathy will be conducted during Screening. The decision to perform an echocardiogram or MUGA will be at the discretion of the Investigator. Additional echocardiograms or MUGA scans may be performed during subsequent visits if clinically appropriate, per Investigator discretion.

A standard 12-lead electrocardiogram (ECG) will be performed. Patients must rest for at least 5 minutes prior to the ECG recording. The Investigator will interpret the ECG using one of the following categories: normal, abnormal but not clinically significant, or abnormal and clinically significant. The date and time the ECG is performed and the following parameters will be recorded in the eCRF: heart rate, PR interval, QT interval, QRS interval, and QT corrected (QTc) using Bazett's formula.

Clinical Laboratory Tests

All safety laboratory assessments will be performed and analyzed at the site's local laboratory.

The following clinical laboratory tests will be performed and assessed at the local laboratory:

- Hematology (blood sample: whole blood) - EDTA tests including Hb, hematocrit, mean corpuscular volume, mean corpuscular Hb, mean corpuscular Hb concentration, WBC count, WBC differential, red blood cell (RBC) count, lymphocytes, monocytes, neutrophils, eosinophils, basophils, and platelets will be performed.
 - WBC differential may be automated or manual as per institutional standards.
- Serum Chemistry (blood sample: serum)
 - Complete Serum Chemistry will include sodium, potassium, chloride, bicarbonate (HCO3-), blood urea nitrogen (BUN), creatinine, glucose, calcium, phosphate, magnesium, ALT, AST, alkaline phosphatase, total bilirubin.

5.3. Minimal residual disease

We will evaluate the status of minimal residual disease (MRD) in patients who achieve sCR, CR, or nCR by 10-color multiparametric flow cytometry. When a patient achieves VGPR or biochemical CR, bone marrow confirmation will be performed to assess for MRD using bone marrow aspirate.

5.4. HBV Serology

All subjects will be tested locally for hepatitis B surface antigen (HBsAg), hepatitis B surface antibody (Anti-HBs), and hepatitis B core antibody (Anti-HBc) at Screening. HBV serology is not required at Screening if this was performed as part of standard of care within 3 months prior to first dose.

5.5. HBV DNA Tests

Subjects who are positive for Anti-HBc or Anti-HBs will undergo testing for hepatitis B DNA by PCR. Subjects with serologic findings suggestive of HBV vaccination (Anti-HBs positivity as the only serologic marker) and a known history of prior HBV vaccination do not need to be tested for HBV DNA by PCR. During and following study treatment, subjects who have history of HBV infection will be closely monitored for clinical and laboratory signs of reactivation of HBV as specified in the Time and Events

Schedule (Table 1). Where required by local law, the results of HBV testing may be reported to the local health authorities.

6. STUDY POPULATION

6.1. Number of participants

This is a multicenter, open label, phase 1b/2 study of patients with relapsed or refractory MM after treatment with Daratumumab (Dara)-based therapy in the second line setting. Patients must have been exposed to a PI, IMiD, and PI and must have had more than 2 or more prior lines of therapy.

This study is anticipated to enroll overall up to 42 patients who fulfill the eligibility criteria (20-32 subjects previously exposed to Dara + Len + Dex; 10-22 subjects previously exposed to Dara + Pom + Dex).

6.2. Inclusion criteria

Subjects must satisfy the following criteria to be enrolled in the study:

1. Documented multiple myeloma with prior exposure to an IMiD, PI, and CD-38 moAb.
2. Patients must have 2 or more prior lines of therapy.
3. Patients must have been previously exposed to:
 - a. Dara+Len+Dex and must have achieved at least stable disease to this combination.
or;
 - b. Dara + Pom + Dex and must have achieved at least stable disease to this combination.
4. Histologically confirmed and relapsed multiple myeloma with measurable disease, defined by at least one of the following:
 - a. Serum monoclonal protein ≥ 0.5 g/dL;
 - b. Monoclonal protein in the urine on 24-hour electrophoresis ≥ 200 mg;
 - c. Serum immunoglobulin free light chain (FLC) ≥ 10 mg/dL (100 mg/L) provided serum FLC ratio is abnormal;
 - d. New or progressing biopsy proven plasmacytoma on exam or imaging; or
 - e. Bone marrow plasma cells $\geq 20\%$;
5. Cycle 1 day 1 of study treatment must be within 3 months of last exposure to Daratumumab.
6. Life expectancy >3 months

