This is a multi-institution phase 1b/2 study of ATRA in combination with fixed dose Daratumumab, Pomalidomide and Dex for patients with relapsed multiple myeloma who have progressed on the combination of Dara + Len + Dex. During the dose escalation phase (phase 1b) and after the first cycle, patients who have not experienced a drug-limiting toxicity (DLT), have not shown signs of progressive disease (PD), and in the opinion of the investigator would continue to benefit from additional Dara + Pom + Dex + ATRA may receive additional cycles of treatment (see section 7.4 for details). The phase 2 portion will allow further enrollment at the maximum tolerated dose (MTD) to further evaluate safety and efficacy.

Study Population

Patients with relapsed or refractory multiple myeloma who have progressed on the combination of Dara + Len + Dex or Dara + Pom + Dex. We will include a maximum of 42 patients (among 20-32 subjects previously exposed to Dara + Len + Dex or 10-22 subjects previously exposed to Dara + Pom + Dex).

Length of Study

The overall study duration is expected to be three (3) years, two years for enrollment, one year to complete follow-up.

Treatment Plan

During 28-day treatment cycles, patients will receive Dara 1800 mg subcutaneous (SC) administration at their current dose upon enrollment onto the study depending on their cycle. (If they are on cycles 1-2

then they will receive Dara 1800 mg SC days 1,8,15,22; if they are on cycles 3-6 they will receive Dara 1800 mg SC days 1 and 15; if they are on cycle 7 or beyond they will receive Dara 1800 mg SC on day 1).

Pomalidomide will be administered at the patient's currently tolerated dose (4,3, or 2 mg po daily) on days 1-21. Patients who are progressing on daratumumab + lenalidomide + dexamethasone will start with the 4 mg dose (standard of care starting dose) of pomalidomide.

Dexamethasone will be administered at 40 mg once weekly on days 1,8,15 for patients 75 years old and younger and at 20 mg once weekly on days 1,8,15 for patients older than 75. Patients may stay on their currently administered steroid regimen if it does not match the above.

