1.6. ATRA in combination with Daratumumab, pomalidomide, and dexamethasone

In the phase 2 single arm study, the response rate of the combination of daratumumab in combination with pomalidomide and dexamethasone was 60%. However, all patients eventually progressed with a median PFS of 8.8 months with a median follow-up of 13.1 months with a median overall survival of 17.5 months (Chari A et al, Blood, 2017). There is a marked heterogeneity of response with 40% of patients achieving less than stable disease to this regimen. Mechanisms of resistance to the combination of daratumumab + pomalidomide + dex are poorly understood. It is hypothesized that it is a combination of loss of CD38 expression as well as host- and tumor-related factors.

An improved understanding of mechanisms that may contribute to innate or acquired resistance may result in the rational design of new daratumumab plus pomalidomide-based combinations with higher antimyeloma activity. All-trans retinoic acid (ATRA) has been shown in mice models even in IMiD and daratumumab-refractory myeloma to improve daratumumab-mediated antibody-dependent cell mediated cytotoxicity (ADCC) and complement mediated cytotoxicity (CDC). Furthermore, in the subgroup of cell lines refractory to IMiDs and daratumumab, ATRA reduced the expression of the complement inhibitors CD55 and CD59 on myeloma cells, thereby further enhancing daratumumab-mediated CDC (Nijhof IS et al, Leukemia, 2015).

Thus, we intend to evaluate the combination of ATRA with daratumumab, pomalidomide, and dexamethasone in patients progressing on daratumumab + IMiD. The hypothesis is that sensitivity to the CD38-mo-Ab, IMiD, dex combination will be restored.

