3. STUDY ENDPOINTS

Primary Endpoints:

Phase 1b: The percentage of patients with treatment emergent adverse events (TEAEs) overall and per dose level.

- Patients with DLTs at each dose level.
- Patients with Grade ≥ 3 TEAEs
- Patient with serious adverse events (SAEs)
- Patients who discontinue because of TEAEs
- Patients with dose modifications (delays, interruptions, dose reductions)
- Clinically significant laboratory values

Phase 2: ORR as defined by IMWG criteria (subjects progressing on Dara + Len + Dex)

Secondary Endpoints:

- 1) ORR as defined by IMWG criteria (subjects progressing on Dara + Pom + Dex)
- 2) Rate of CR, sCR, or nCR
- 3) Rate of VGPR
- 4) TTP
- 5) DOR
- 6) PFS using Kaplan Meier
- 7) OS using Kaplan Meier

Exploratory Endpoints:

Explorative endpoints of samples collected before, during and after treatment with Dara + ATRA, + Pom + Dex and include but are not limited to the following:

- 1) Gut Microbiome analysis
- 2) Immune cell subset analyses
- 3) Analyses of cytokine, chemokine, inflammatory/anti-inflammatory and bacterial translocation markers
- 4) Basic peripheral blood laboratory variables
- 5) Genetic and epigenetic profiles

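### Inclusion criterion 3 requires exposure to Dara+Len+Dex or Dara+Pom+Dex, not progression on it, so patients outside the stated primary population can enter and be counted in the Dara+Len+Dex group

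*Combined protocol and SAP*

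**What the plan says.** Several places describe a population that has progressed on a named regimen. Section 3 gives the primary endpoint as "Phase 2: ORR as defined by IMWG criteria (subjects progressing on Dara + Len + Dex", and the phase 2 primary objective in section 2 matches it. Section 1.6 places the hypothesis of restored sensitivity "in patients progressing on daratumumab + IMiD". The synopsis, under Study Population, describes patients "who have progressed on the combination of Dara + Len + Dex or Dara + Pom + Dex".

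The criteria that decide entry are worded differently. In section 6.2, and identically in the synopsis:

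- Criterion 3 opens with "Patients must have been previously exposed to" and then offers two alternatives: "Dara+Len+Dex and must have achieved at least stable disease to this combination", or "Dara + Pom + Dex and must have achieved at least stable disease to this combination".
- Criterion 4 asks for "Histologically confirmed and relapsed multiple myeloma with measurable disease" and does not link the relapse to a regimen.
- Criterion 5 states "Cycle 1 day 1 of study treatment must be within 3 months of last exposure to Daratumumab". Any daratumumab regimen satisfies it.

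No exclusion criterion in section 6.3 adds a progression requirement. Section 6.1 counts enrolment by exposure (20-32 Dara+Len+Dex, 10-22 Dara+Pom+Dex, at most 42 in all). The synopsis, under Primary Analysis, groups the subset ORR by previous exposure. Section 9.3 names ORR as the primary efficacy parameter without saying which patients form the denominator. Section 5.1 has the progression date of every prior regimen entered in the eCRF, but neither the eligibility criteria nor the analysis section uses it.

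**The concern.** The trial asks whether adding ATRA restores response in disease that has become resistant to daratumumab plus an IMiD. Two kinds of patient can meet all the criteria without belonging to the stated primary population:

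- a patient who stopped Dara+Len+Dex for a reason other than progression and relapsed off it, still within 3 months of the last daratumumab dose;
- a patient who had Dara+Len+Dex earlier, did not progress on it, and whose latest relapse was on a different daratumumab regimen.

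Both would be counted as exposed to Dara+Len+Dex. If their disease is not resistant to that regimen, some could respond without any contribution from ATRA, and a single-arm trial cannot separate the two.

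Assignment is also open. Criteria 3a and 3b are joined by "or" and do not exclude each other, while the enrolment ranges pair to the maximum (20 + 22 = 42 and 32 + 10 = 42), which presumes separate groups. One group carries the primary endpoint and the other a secondary endpoint. No rule places a patient exposed to both regimens. The trial is open label with investigator-assessed response (section 4.1), so this should be settled before outcomes are known.

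**Working it through.** **1. Reproduce the plan's design.** Section 9.2: 10 patients in stage 1, continue with 3 or more responses; success with 8 or more of 20; null 25%, alternative 48%, one-sided 0.10. For a true response rate p,

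P(success) = Σ over x = 3 to 10 of C(10,x) p^x (1−p)^(10−x) × P(Y ≥ 8 − x), with Y ~ Binomial(10, p).

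- p = 0.25: 0.0956 (the plan states 0.096).
- p = 0.48: 0.8059 (the plan states 0.806).
- Early stopping at 0.25: 0.75^10 + 10(0.25)(0.75^9) + 45(0.25²)(0.75^8) = 0.0563 + 0.1877 + 0.2816 = 0.5256 (the plan states about 52.0%).

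The error rate and power reproduce, so the same formula can be used for what follows.

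**2. Mixed population.** Let f be the share of patients who did not progress on the named regimen and q their ORR, with progressors at the null of 25%. The overall rate is p = 0.25(1 − f) + q f. For example, f = 0.20 and q = 0.48 give 0.200 + 0.096 = 0.296.

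The documents give neither f nor q, so both are assumptions. I take f = 10%, 20% and 30%; in 20 patients, 10% is two people. I take q = 40%, 48% (the design alternative) and 60%. The last is the Dara+Pom+Dex ORR that the protocol cites from a phase 2 study in patients with at least two prior therapies, used here as an upper case.

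**3. Chance of declaring success (mixed ORR in brackets).**

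| Assumed ORR of non-progressors | f = 10% | f = 20% | f = 30% |
|---|---|---|---|
| 25% | 0.096 (25.0%) | 0.096 (25.0%) | 0.096 (25.0%) |
| 40% | 0.126 (26.5%) | 0.161 (28.0%) | 0.201 (29.5%) |
| 48% | 0.144 (27.3%) | 0.204 (29.6%) | 0.274 (31.9%) |
| 60% | 0.174 (28.5%) | 0.277 (32.0%) | 0.398 (35.5%) |

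With f = 0 the value is 0.096.

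**4. The other design in the document.** The synopsis prints a different Simon design: 12 then 28 patients, null 30%, stop at 4 or fewer of 12, success at 12 or more of 28. As printed, that rule has an exact error of 0.078 at 30%. With f = 20% and q = 40% to 60% it becomes 0.117 to 0.224. The pattern is the same under either rule. The conflict between the two designs is a separate matter and must be reconciled on its own.

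**The case against.** The strongest reply is that the gap is narrow and the endpoint wording already closes it.

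- *Criteria 4 and 5 restrict entry to relapsed, measurable disease within 3 months of daratumumab.* This stands. Most entrants have probably progressed on or soon after a daratumumab regimen, and the share of others may be small.
- *Read literally, the endpoint leaves a non-progressor out of the primary ORR, and section 5.1 collects the date needed to apply it.* This is a fair reading. However, section 9.3 does not state that analysis set, and the groupings the plan does state are by exposure. An analyst following those groupings would include the patient.
- *A patient who relapsed on another daratumumab regimen may be as resistant as the target population.* This also stands. Section 1.5 reports that CD38 expression fell after daratumumab began and rose again about 6 months after it was stopped, so the 3-month limit admits patients before that recovery. Against this, section 1.5 reports that CD55 and CD59 rose only at progression, so the resistance mechanism is partly absent in a patient who did not progress.
- *The dosing text in section 4.1 distinguishes patients progressing on Dara+Len+Dex from those with a currently tolerated pomalidomide dose, which hints at assignment by current regimen.* It is only a hint, and it does not settle dual exposure.

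A reader might infer that the criteria will raise the ORR and double or quadruple the false-success rate. The documents do not support that: the shares and response rates are assumed, the low case moves 0.096 only to 0.126, and there is no change if these patients respond at 25%. Nor do they show a deliberate choice to study non-progressors; the synopsis and section 4.1 both describe progressing patients.

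**Conclusion.** The criteria and the exposure groupings do not match the stated primary population. Followed as written, they can put patients who did not progress on Dara+Len+Dex into a decision resting on about 20 patients, and they leave dual-exposed patients unassigned. The possible effect is a biased primary ORR, plausibly upward; misassignment of dual-exposed patients could move it either way.

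Under the section 9.2 rule with progressors at 25%, and an assumed ORR of 40% to 60% in the others, the chance of declaring success is 0.126-0.174 at a 10% share, 0.161-0.277 at 20% and 0.201-0.398 at 30%. These are scenarios, not estimates. The mismatch itself rests on the text alone and needs none of these assumptions.

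**What to change.** Reconcile criterion 3, in both the synopsis and section 6.2, with the stated population. Either of two changes would do it:

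1. Require documented IMWG progression on the named regimen as part of criterion 3.
2. Keep the criterion, and define the primary ORR analysis set in section 9.3 as patients whose recorded progression date (section 5.1) shows progression on Dara+Len+Dex. Report all others separately.

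In either case, pre-specify one cohort per patient, recorded at enrolment, by the named regimen on which the patient most recently progressed. Use the same definition for the enrolment counts and the subset ORR. A patient who progressed on Dara+Pom+Dex and later on Dara+Len+Dex would then fall in the primary cohort. That agrees with the endpoint wording, but it should be stated openly.

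The cost is a wording change and no new data collection. The first option slightly narrows the accrual pool at a two-site study. The second slightly reduces the primary analysis set, so the plan should say that the stage counts of 10 and 20 refer to patients in that set.

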APPENDIX B: International Myeloma Working Group Uniform Response Criteria 2016

Table 9: International Myeloma Working Group Uniform Response Criteria

Response Category	Response Criteria*
MRD response Criteria (requires a complete response)	
Sustained MRD-negative	MRD negativity in the marrow (NGF or NGS, or both) and by imaging as defined below, confirmed minimum of 1 year apart. Subsequent evaluations can be used to further specify the duration of negativity (eg, MRD-negative at 5 years) †
Flow MRD-negative	Absence of phenotypically aberrant clonal plasma cells by NGF‡ on bone marrow aspirates using the EuroFlow standard operation procedure for MRD detection in multiple myeloma (or validated equivalent method) with a minimum sensitivity of 1 in 10^5 nucleated cells or higher
Sequencing MRD-negative	Absence of clonal plasma cells by NGS on bone marrow aspirate in which presence of a clone is defined as less than two identical sequencing reads obtained after DNA sequencing of bone marrow aspirates using the LymphoSIGHT platform (or validated equivalent method) with a minimum sensitivity of 1 in 10^5 nucleated cells§ or higher
Imaging plus MRD-negative	MRD negativity as defined by NGF or NGS plus disappearance of every area of increased tracer uptake found at baseline or a preceding PET/CT or decrease to less mediastinal blood pool SUV or decrease to less than that of surrounding normal tissue¶
Standard IMWG response criteria	
Stringent Complete Response (sCR)	Complete response (CR) as defined below, plus Normal serum free light chain (FLC) ratio** and Absence of clonal plasma cells by immunohistochemistry (κ/λ ratio $\leq 4:1$ or $\geq 1:2$ for κ and λ patients, respectively, after counting ≥ 100 plasma cells)††
Complete Response (CR)	Negative immunofixation of serum and urine and Disappearance of any soft tissue plasmacytomas and $< 5\%$ plasma cells in bone marrow aspirates In patients in whom the only measurable disease is by serum FLC levels: CR

	in such patients indicates a normal FLC ratio of 0.26 to 1.65 in addition to CR criteria listed above.

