Very Good Partial Response (VGPR)	
Serum and urine M-protein detectable by immunofixation but not on electrophoresis
 
or
 
90% or greater reduction in serum M-protein plus urine M-protein level <100 mg per 24 hours
 
In patients in whom the only measurable disease is by serum FLC levels: VGPR in such patients requires a > 90% decrease in the difference between involved and uninvolved FLC levels.

Table 9: International Myeloma Working Group Uniform Response Criteria (Continued)

Response Category	Response Criteria*
Partial Response (PR)	
$\geq 50\%$ reduction of serum M-Protein and reduction in 24-hour urinary M-protein by $\geq 90\%$ or to < 200 mg per 24 hours
 
If the serum and urine M-protein are not measurable, a $\geq 50\%$ decrease in the difference between involved and uninvolved FLC levels is required in place of the M- protein criteria.
 
If serum and urine M-protein are unmeasurable, and the serum free light chain assay is also unmeasurable, a $\geq 50\%$ reduction in plasma cells is required in place of M- protein, provided baseline bone marrow plasma cell percentage was $\geq 30\%$
 
In addition to these criteria, if present at baseline, a $\geq 50\%$ reduction in the size measured by sum of the products (SPD) §§ of the maximal perpendicular diameters of soft tissue plasmacytomas is also required

Stable Disease (SD)	Not meeting criteria for CR, VGPR, MR, PR, or progressive disease (PD)
Progressive disease (PD) 	
Requires only one of the following:
 
Increase of 25% from lowest response value in any of the following:
 
 • Serum M-component (absolute increase must be ≥ 0.5 g/dL), and/or • Urine M-component (absolute increase must be ≥ 200 mg/24 h), and/or 
Only in patients without measurable serum and urine M-protein levels: the difference between involved and uninvolved FLC levels (absolute increase must be ≥ 10 mg/dL)
 
Only in patients without measurable serum and urine M protein levels and without measurable disease by FLC levels, bone marrow plasma cell percentage (absolute increase must be $\geq 10\%$)
 
Appearance of a new lesion(s), $\geq 50\%$ increase from nadir in SPD §§ of > 1 lesion, or
 
$\geq 50\%$ increase in the longest diameter of a previous lesion > 1 cm in short axis;
 
$\geq 50\%$ increase in circulating plasma cells (minimum of 200 cells per μL) if this is the only measure of disease

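### Inclusion criteria 4d and 4e admit some patients for whom the printed Table 9 has no route to partial response, so ORR in the Dara+Len+Dex cohort may be somewhat understated

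*Combined protocol and SAP*

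**What the plan says.** **Entry.** Section 6.2, criterion 4, and the matching Synopsis list require one or more of five measures. Items 4a to 4c are serum M-protein, urine M-protein and serum FLC, each with a numeric threshold. Item 4d is "New or progressing biopsy proven plasmacytoma on exam or imaging; or", with no marrow minimum. Item 4e is "Bone marrow plasma cells $\geq 20" per cent.

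**Response.** In Appendix B, Table 9, the PR row works through M-protein, then FLC if M-protein is not measurable, then marrow plasma cells if FLC is not measurable either. The marrow step applies only "provided baseline bone marrow plasma cell percentage was $\geq 30" per cent. Plasmacytoma shrinkage is introduced by "In addition to these criteria, if present at baseline", so it adds to the other requirements and does not replace them. A patient who meets no other category falls into the stable disease row.

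**Progression.** The same table reaches these patients through marrow ("without measurable disease by FLC levels, bone marrow plasma cell percentage (absolute increase must be $\geq 10" per cent) and through lesions ("Appearance of a new lesion(s") or lesion growth. Neither has a baseline marrow floor.

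**Counting.** The phase 2 primary endpoint is ORR in subjects progressing on Dara+Len+Dex (Section 3). Section 9.2 enrols about 20 eligible patients and declares success at 8 or more responses among the 20. It defines evaluability and replacement for phase 1b only. Section 9.3 names no efficacy analysis set, and Section 9.4 names one for safety only.

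**The concern.** The entry rule and the response rule use different marrow thresholds, 20% and 30%, and treat plasmacytoma differently: sufficient for entry, but not sufficient for PR. A patient whose marrow falls from 25% to 10%, or whose only plasmacytoma halves in size, could be benefiting and still be scored as stable disease. The same patient could be scored as progressing without difficulty.

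Such a patient stays in the denominator of a 20-patient Simon design with a reduced chance of entering the numerator. What is at stake is wrongly dropping an active combination, possibly at the 10-patient futility look. Only patients in the Dara+Len+Dex group bear on the primary endpoint. Affected Dara+Pom+Dex patients touch only the secondary ORR, provided the Simon count follows the endpoint as stated.

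**Working it through.** **Step 1. Who is affected.** I take ORR to mean PR or better, and infer from 4a to 4c what Table 9 means by measurable.

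| Qualifying disease (no usable serum, urine or FLC marker) | Printed PR route? |
|---|---|
| Marrow only, 30% or more | Yes, marrow reduction |
| Marrow only, 20% to under 30% | No |
| Plasmacytoma, marrow 30% or more | Yes, marrow reduction plus shrinkage |
| Plasmacytoma, marrow under 30% | No |

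CR stays open to the two affected groups: negative immunofixation, no plasmacytoma, and under 5% "plasma cells in bone marrow aspirates". Whether the first VGPR limb ("detectable by immunofixation but not on electrophoresis") could apply to a patient with no measurable M-protein at baseline is unclear.

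**Step 2. Reproduce Section 9.2.** Inputs: 10 patients in stage 1, continue at 3 or more; 10 more in stage 2, success at 8 or more of 20; null rate 25%, target 48%. With X1 and X2 the responses in each stage,

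P(success) = sum over x = 3 to 10 of P(X1 = x) × P(X2 ≥ 8 − x).

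At 48%, the terms are 0.1364 × 0.5730 (x=3), 0.2204 × 0.7933 (x=4), 0.2441 × 0.9298 (x=5), 0.1878 × 0.9852 (x=6), 0.0991 × 0.9986 (x=7), and 0.0419 for x = 8 to 10. They sum to **0.806**, the stated power. At 25% the result is 0.096, the stated type I error. The chance of stopping at stage 1 when the true rate is 48% is 0.070.

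**Step 3. One affected patient.** Let that patient respond with probability q and everyone else with probability 0.48. In stage 1 with q = 0, X1 is binomial on 9 patients: 0.1837 × 0.5730 + 0.2543 × 0.7933 + 0.2347 × 0.9298 + 0.1445 × 0.9852 + 0.0571 × 0.9986 + 0.0146 = **0.739**. In stage 2 with q = 0 the result is **0.758**. With one affected patient, power is linear in q and returns to 0.806 at q = 0.48. For example, at q = 0.35 in stage 1: 0.7392 + (0.35/0.48) × (0.8059 − 0.7392) = 0.788.

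| q | One in stage 1 | One in stage 2 | One in each stage | Stage 1 stop, one in stage 1 |
|---|---|---|---|---|
| 0 (worst case) | 0.739 | 0.758 | 0.683 | 11.1% |
| 13.6% | 0.758 | 0.771 | 0.719 | 10.0% |
| 25% | 0.774 | 0.783 | 0.749 | 9.0% |
| 35% | 0.788 | 0.793 | 0.774 | 8.1% |

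The documents give neither q nor the number affected. The 13.6% is the rate of CR or better in the Dara+Pom+Dex study cited in the Introduction, a different population. The other values are assumed.

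**Step 4. Direction.** With 25% in the others and q = 0 for one patient, type I error falls from 0.096 to 0.071 (stage 1) or 0.074 (stage 2). The error is conservative.

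**The case against.** - **The documents do score and count these patients.** This is correct. The stable disease row catches anyone not otherwise classified, and Section 9.2 counts eligible patients. A reader might infer that the plan is silent on them. It is not: read literally, it applies a conservative rule. What remains is that this rule fits poorly with an entry criterion that calls the same disease measurable.
- **The gap depends on what measurable means.** Table 9 prints no cut-off, and its first PR limb sets no minimum M-protein. A 4d or 4e patient with M-protein below 0.5 g/dL might be scored PR on a literal reading. This stands, so the gap is firm only for patients with no usable serum, urine or FLC marker.
- **Text not supplied may close it.** Table 9 refers to the full IMWG criteria, and Section 9.1 leaves detailed methods to the SAP. Either might settle the matter, but neither is reproduced. Section 4.1 also names an earlier base version of the criteria than the Appendix B title does.
- **The power loss is assumed.** Section 9.2 gives 48% as the true response rate without setting any patients aside. If it already describes everyone whom criterion 4 admits, there is no loss against plan. This stands as a condition on the figures.
- **Counting every eligible patient is defensible.** It is, and for that reason the point does not call for replacing the primary count with a response-evaluable set.

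**Conclusion.** The mismatch is on the page, but it is narrow. It concerns patients with no usable serum, urine or FLC marker and baseline marrow under 30%, who enter on a plasmacytoma or on marrow of 20% to under 30%. Their chance of being scored a responder is reduced, so ORR in the Dara+Len+Dex cohort tends to be understated.

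Under the Section 9.2 design, with 48% in the other patients, one such patient takes power from 0.806 to 0.74-0.76 if response is impossible, or to 0.79 if its chance is 35%. The loss is zero if none enrols or if 48% already allows for them. These figures do not carry over to the different Simon design printed in the Synopsis.

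Three stronger readings are tempting and unsupported. A reader might infer that these patients can never respond, but CR is open to them and VGPR may be. A reader might infer that every patient entering on 4e alone is affected, but those with marrow of 30% or more have a printed PR route. A reader might infer a risk of a false positive result, but the effect runs the other way. This is a cheap improvement to consider, not a flaw that invalidates the design.

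**What to change.** **Preferred.** For the phase 2 primary cohort, reconcile criterion 4 (Section 6.2 and Synopsis) with Appendix B by requiring at least one baseline measure that has a printed PR route: 4a, 4b, 4c, or marrow of 30% or more. Patients who qualify on 4e alone with marrow of 30% or more stay in.

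**Otherwise.** Before any response data are seen, state in Appendix B and Section 9.3 how plasmacytoma-only patients, and marrow-only patients at 20% to under 30%, are scored. Report ORR with and without them. Fixing this in advance matters because the trial is open-label and response is assessed by the investigator.

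Phase 1b eligibility need not change under either option.

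**Cost.** A few lines of text. A few patients would be excluded from the primary cohort or listed separately from it, and accrual may be slightly slower.
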